## 10.3 Treatment Compliance and Exposure

### 10.3.1 Treatment Compliance

Compliance with administration of study drug will be assessed at each study visit post-randomization during the Treatment Period and at the ET Visit, if applicable. Compliance will be computed using information collected on the Study Drug Interruption CRF. Specifically, compliance will be calculated for each subject at each scheduled post-randomization visit during the treatment period (and the ET visit, if applicable) as (number of tablets taken since last visit/number of tablets that should have been taken since last visit)\*100. Treatment period is defined as the time period from first dose date to last dose date. As each subject is instructed to take 2 tablets per day during the treatment period, the number of tablets that should have been taken since the last visit will be computed as 2 tablets per day\*number of days since last visit, where the number of days since the last visit will be computed as (day of visit - day of last visit + 1) for the second visit (Week 2 or ET), and (day of visit - day of last visit) for all subsequent visits (up to Week 12). Compliance will be summarized by visit by actual treatment group for the SAS.

For each subject, overall compliance will be computed as (number of tablets taken during treatment period/number of tablets that should have been taken during treatment period)\*100. The number of tablets that should have been taken during the treatment period will be computed as 2 tablets per day\* number of days during the treatment period, where the number of days during the treatment period will be computed as (last dose date – first dose date + 1). Subjects will then be grouped into categories of overall compliance (< 80%, 80% to 100%) according to their overall estimate of compliance. Overall compliance and categories of compliance will be summarized using descriptive statistics (n, mean, median SD, minimum, maximum for overall compliance, and frequencies and percentages for categories of compliance) by actual treatment group for the SAS.

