## APPENDIX A: SCHEDULE OF PROCEDURES

	Pre-Screening a	Screening b,f				Treatment Period c				Follow-Up d	ET
		Study Day -28 to -21	Study Day -14 to -7	Study Day-7	Study Day 1 e	Week 2/ Study Day 15±3 days	Week 6/ Study Day 43±3 days	Week 10/ Study Day 71±3 days	Week 12/ Study Day 85 or up to 3 days prior to Study Day 85	Study Day 113	
	Visit Identifier	Visit S1	Visit S2	Visit S3	Visit T1	Visit T2	Visit T3	Visit T4	Visit T5	Visit FU1	
Informed consent	X	X									
Inclusion/exclusion criteria	X	X	X	X	X						
Medical/surgical history and demographics	X	X	X	X	X						
Full physical examination g	X	X							X		X
Symptom-directed physical examination		X h			X	X	X	X		X i	
Vital signs j , height k , and weight	X	X	X	X	X	X	X	X	X		X
Body Mass Index (BMI)	X	X			X			X	X		X
Waist circumference					X				X		X
Urinalysis + NAGL l	X	X			X		X		X	X i	X
Protein:creatinine ratio; albumin:creatinine ratio	X	X			X		X		X	X i	X
Serum/urine pregnancy test m	X	X			X	X	X	X	X	X i	X
Safety chemistry panel, coagulation, and hematology n	X	X	X	X	X	X	X	X	X	X i	X
TSH and serology o	X	X f									
Fasting lipid panel p	X q	X	X	X	X	X	X	X	X	X	X
Fasting apolipoproteins r					X			X	X	X	X
LDL-C ultracentrifugation (LDL-C, LDL-TG, VLDL-TG)					X			X	X	X	X
Cl ██████████					X				X		X
HbA1c	X	X			X				X		X
Cystatin-C, ANGPTL4, adiponectin					X				X		X

hsCRP, SAA, IL-6, and fibrinogen					X			X	X		X
Lipoprotein size and particle number					X				X		X
Randomization					X						
Study drug administration s					X	X	X	X			
Dispense study drug and instructions					X	X	X	X			
Compliance check						X	X	X	X		X
Distribute drug diary					X	X	X	X			
Dietary assessment (self-reported) t	X	X	X	X	X	X	X	X			
12-lead ECG u		X			X	X	X	X	X		X
Initiate wash-out	X										
Adverse events	X v	X v	X	X	X	X	X	X	X	X	X
Concomitant medications	X	X f	X	X	X	X	X	X	X	X	X
Reserve serum samples w					X	X	X	X	X		X
Reserve plasma PK samples x					X	X	X	X	X		X
Collect drug diary						X	X	X	X		X
Reserve genotyping sample					X						

Footnotes appear on the following page

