## **8.2 Per-Protocol Set**

The Per Protocol Set (PPS) will be determined partially through sponsor review of blinded individual subject data and partially through objective criteria. Both methods will be completed prior to database lock. The following criteria for FAS subjects should be met in order to qualify for the PPS:

- Subjects completed the 12-week Treatment Period
- Subjects taking a statin in combination with study drug did not experience a change or interruption in statin dose
- Subjects took the same study drug medication for the entire study duration and it matches the treatment to which they were randomized

Additionally, a sponsor review for any other major protocol deviations that may impact efficacy (such as low study medication compliance [i.e., approximately 80% or lower] after Week 6) will be conducted, and further subjects could be excluded from the PPS. The PPS will be used to assess robustness of the analysis results. Subjects excluded from the PPS and the reason for exclusion will be provided in the listings.

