### 10.3.2 Treatment Exposure

Duration of exposure will be calculated for each subject as (last dose date – first dose date + 1) and will be summarized using descriptive statistics (n, mean, median, SD, minimum, maximum). The number of subjects who receive  $\geq$  1 day,  $\geq$  7 days,  $\geq$  14 days,  $\geq$  28 days,  $\geq$  42 days,  $\geq$  56 days,  $\geq$  70 days, and  $\geq$  84 days of the study medication will be presented by actual treatment group for the SAS.

Days on treatment will be computed as the number of days that the study medication was taken (ie, duration of exposure minus days when the study medication was interrupted). Number of days on treatment and number of days study medication was interrupted will also be summarized for the SAS.

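### By-visit compliance in SAP 10.3.1 counts tablets as due after the last dose, which distorts early-termination rows and, if no dose is due on that visit day, the Week 12 row

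*SAP*

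**What the plan says.** SAP 10.3.1 defines two compliance measures on different time spans.

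- **By visit.** Tablets taken since the last visit are divided by tablets that should have been taken. The denominator is two tablets times a number of days: "day of visit - day of last visit + 1) for the second visit (Week 2 or ET" for the first interval, "and (day of visit - day of last visit) for all subsequent visits (up to Week 12" for the later ones. The rule covers ET visits and does not mention the last dose.
- **Overall.** "the number of days during the treatment period will be computed as (last dose date – first dose date + 1".
- **Treatment period.** "Treatment period is defined as the time period from first dose date to last dose date". Tablets are expected only within it: "As each subject is instructed to take 2 tablets per day during the treatment period".

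The numerator is said to come from the Study Drug Interruption CRF. The SAP does not say how tablets taken in an interval are derived from it.

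The documents differ on whether a dose is due on the Week 12 visit day. Protocol 6.4.5 lists no drug administration at that visit. The row "Study drug administration" in Protocol Appendix A, and the same row in SAP Appendix 1, is marked at T1 to T4 only. Protocol 5.5.3, however, has drug given at the site on clinic visit days without excepting Week 12, and SAP Table 1 runs the treatment period through Day 85.

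SAP 8.2 lets the sponsor consider "low study medication compliance [i.e., approximately 80% or lower] after Week 6" when settling the Per-Protocol Set (PPS).

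**The concern.** The by-visit denominator can include days on which the plan's own definition says no tablet was due. There are two such cases: the days between the last dose and a later ET visit, and the Week 12 visit day if no dose is due then. Protocol 8.1.4.4 shows that the first case is built into the design: drug is stopped, the ET visit follows, and no maximum gap is given.

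A subject who took every tablet could then appear in the by-visit table as partly non-compliant while the overall figure is 100%. Because the numerator is not defined, two programmers could also report different values for the same subject. By-visit compliance might in addition inform the PPS review, and the PPS analysis is one of the two sensitivity analyses of the primary endpoint (SAP 11.2).

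**Working it through.** The documents state no compliance figure, so there is none to reproduce. The check applies the SAP 10.3.1 formulas to a subject who takes two tablets on every day a dose is due.

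**Inputs.** Nominal visit days are 1, 15, 43, 71 and 85 (Protocol Appendix A). Week 10 may fall on Days 68 to 74 and Week 12 on Days 82 to 85 (Protocol 6.4.4 and 6.4.5). At Weeks 2, 6 and 10 the visit-day dose is taken after the blood draw (Protocol 5.5.4 and 6.4.2 to 6.4.4). No Week 12 visit-day dose is assumed here, so the last dose is on Day 84.

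**Step 1. Completer, nominal days, numerator = tablets actually taken.**

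| Visit | Days in denominator | Taken / expected | Compliance |
|---|---|---|---|
| Week 2 | 15 - 1 + 1 = 15 | 30/30 | 100% |
| Week 6 | 43 - 15 = 28 | 56/56 | 100% |
| Week 10 | 71 - 43 = 28 | 56/56 | 100% |
| Week 12 | 85 - 71 = 14 | 26/28 | 92.9% |
| Overall | 84 - 1 + 1 = 84 | 168/168 | 100% |

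The four intervals sum to 15 + 28 + 28 + 14 = 85 days, against 84 days in the overall measure.

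**Step 2. Allowed windows.** The Week 12 value is (T5 - T4 - 1)/(T5 - T4). The lowest is 7/8 = 87.5% (Days 74 and 82) and the highest is 16/17 = 94.1% (Days 68 and 85).

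**Step 3. ET visit after the last dose.** Take the last visit on Day 43 and the last dose on Day 50. The gaps are assumptions, because the documents give none. The value is (50 - 43)/(ET day - 43):

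- ET Day 50 (no gap): 7/7 = 100%
- ET Day 53: 7/10 = 70%
- ET Day 57: 7/14 = 50%

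Overall compliance is 100% in all three.

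**Step 4. Alternative numerator, expected minus interrupted tablets.** A subject with no interruption scores 100% in every row. At Week 12, however, 28 tablets are credited when 26 were due. At ET on Day 57, 28 are credited when 14 were due.

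**Step 5. PPS mark of about 80%.** Assume two missed days, both in the last interval. Read on that interval alone, the formula gives 11/14 = 78.6% against 11/13 = 84.6% on days due. Read over Days 44 to 84, it gives 39/42 = 92.9% against 39/41 = 95.1%.

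**The case against.** There are four arguments on the other side.

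**The numerator is not stated.** If it is expected minus interrupted tablets, a full taker scores 100% at Week 12 and ET. With two missed days the Week 12 value is 12/14 = 85.7% against 11/13 = 84.6%, about one point apart. This stands, so a flat statement that full takers must score below 100% goes too far. It does not rescue the formula, because the 100% is reached by crediting tablets that were never due. SAP 10.3.2 computes days on treatment as exposure minus interruption days, with exposure ending at the last dose. That favours the first reading but does not define by-visit compliance.

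**A Day 85 dose may be due.** Protocol 5.5.3 and SAP Table 1 can be read that way, and the nominal Week 12 row would then be 28/28. The visit list and both schedules point the other way. The Week 12 part is therefore conditional. The ET part holds under either reading.

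**The PPS is barely touched.** A reader might infer that the ET values, or two missed days, would wrongly remove subjects from the PPS. ET subjects already fail the 12-week completion criterion in SAP 8.2, so their compliance values cannot change membership. The 80% mark is approximate, is applied by sponsor judgement, and is not tied to the Week 12 interval alone. Over Days 44 to 84, a subject would need eight missed days to straddle it (33/42 = 78.6% against 33/41 = 80.5%). This objection stands.

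**The top exposure category is sound.** A reader might carry the point over to SAP 10.3.2, where the number reaching "84 days of the study medication will be presented by actual treatment group", and argue that completers seen on Days 82 to 84 are miscounted. They are not: a subject with 81 to 83 days of drug did not receive 84, and the table says so. How many completers fall short depends on actual visit dates, which the documents do not give.

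**Conclusion.** The inconsistency within SAP 10.3.1 is real and its effect is small. The by-visit rule counts calendar days with no stop at the last dose, which conflicts with the section's own treatment period and its overall measure.

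- **ET rows:** wrong whenever the visit falls after the last dose. The size depends on the gap, and the 70% and 50% examples rest on assumed gaps of 3 and 7 days.
- **Week 12 row:** about 7 points too low on nominal days, provided that no dose is due on the visit day and the numerator is tablets actually taken.
- **Not affected:** Weeks 2, 6 and 10 for subjects still on drug, overall compliance, and its two categories.
- **PPS:** an effect is possible only if the sponsor review reads the Week 12 interval by itself. The documents do not say that it does.

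**What to change.** 1. In SAP 10.3.1, define days due in each interval as max(0, min(visit day, last dose day) - day of last visit), with +1 in the first interval. Report compliance as not applicable when this is 0.
2. Define tablets taken over the same days: 2 x (days due - interruption days). Use these figures in the PPS review.
3. Reconcile Protocol 5.5.3 and SAP Table 1 with Protocol 6.4.5 and the two schedules on whether a dose is due on the Week 12 visit day. The formula works under either answer.

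Check: Week 12 becomes min(85, 84) - 71 = 13 days, 26/26 = 100%. The ET Day 57 example becomes 50 - 43 = 7 days, 14/14 = 100%. If dosing stops before a scheduled visit (last dose Day 40, visits on Days 15 and 43, ET Day 50), the intervals are 15, 25 and 0 days. They sum to 40, which equals 40 - 1 + 1. The floor at zero is needed, because without it the last interval would be 40 - 43 = -3.

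The cost is a wording change in the SAP, a line or two of derivation code, and a short clarification of the Week 12 dosing text. The last dose date is already used in SAP 10.3.1 and 10.3.2, so no new data are needed. The exposure categories in SAP 10.3.2 need no change.

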### 10.3.2 Treatment Exposure

Duration of exposure will be calculated for each subject as (last dose date – first dose date + 1) and will be summarized using descriptive statistics (n, mean, median, SD, minimum, maximum). The number of subjects who receive  $\geq$  1 day,  $\geq$  7 days,  $\geq$  14 days,  $\geq$  28 days,  $\geq$  42 days,  $\geq$  56 days,  $\geq$  70 days, and  $\geq$  84 days of the study medication will be presented by actual treatment group for the SAS.

Days on treatment will be computed as the number of days that the study medication was taken (ie, duration of exposure minus days when the study medication was interrupted). Number of days on treatment and number of days study medication was interrupted will also be summarized for the SAS.

## 11 EFFICACY PARAMETERS

### 11.1 Primary Analysis

The primary efficacy endpoint (percent change in fasting serum TG from baseline to EOS) will be analyzed using ANCOVA on rank-transformed data (i.e., ranked ANCOVA) with percent change from baseline to EOS in TG (converted to ranks) as the dependent variable; treatment and baseline statin (yes or no) as factors; and ranked baseline fasting serum TG as a covariate. The ranked ANCOVA is used due to the expected non-normality historically observed with triglyceride data. The primary analysis will be performed using the FAS. The null hypotheses to be tested are the following:

- $H_1$ : there is no difference in the percent CFBL to EOS in fasting serum TG between gemcabene 300 mg and Placebo
- $H_2$ : there is no difference in the percent CFBL to EOS in fasting serum TG between gemcabene 600 mg and Placebo

A 2-sided test with a significance level of 0.05 will be used for the comparison of the gemcabene 300 mg and 600 mg groups separately to the placebo group. No statistical adjustment will be performed for multiplicity in this Phase 2 study. Note that EOS is defined using LOCF as indicated in [Section 9.4](#). The median, interquartile range, and associated p-value from the ranked ANCOVA will be presented for each treatment group.

```
proc glm data=data;
  class TRT(ref="Placebo") Statin;
  model r_pctCFBL = TRT Statin r_Base / solution;
  lsmeans TRT / stderr pdiff;
run;
```

Where a ranked ANCOVA is used, ranking will be done on the outcome variable and baseline covariate. All values will be ranked by visit regardless of treatment group, with ties receiving the average of the ranks.

Ranked ANCOVA is generally used when the statistical assumptions for parametric ANCOVA, including normality and homoscedasticity (equal variances), are not met, therefore these formal assumptions will not be checked for the ranked ANCOVA analyses. The assumption of homogeneity of regression slopes across treatment groups (parallel slopes) will be investigated by including the interaction between baseline fasting serum TG and treatment group in the model explicated previously. If results indicate that the interaction between baseline fasting serum TG and treatment group is not significant, the assumption of parallel slopes will be considered met. If the assumption of parallel slopes is clearly violated, the final model may be adjusted.

Although qualifying TG ( $> 880$  mg/dL or  $\leq 880$  mg/dL) is a stratification variable, it will not be included in the primary model or any model with TG as the dependent variable, since baseline TG (ranked) is already included in these models as a covariate. Baseline TG and qualifying TG stratum are expected to be highly correlated and could lead to multicollinearity and variance inflation within the model. Therefore, only ranked baseline TG will be used to adjust for TG.

Placebo-corrected median TG change from baseline to EOS estimates (Gemcabene 300 mg vs Placebo; and Gemcabene 600 mg vs Placebo) as well as their corresponding 95% confidence intervals will be obtained using the Hodges-Lehmann Estimate.

Descriptive statistics will also be provided by visit.

## 11.2 Sensitivity Analysis

A sensitivity analysis of the primary LOCF analysis will be performed using the same ranked ANCOVA as the primary analysis, only for this analysis, all subjects from the FAS who discontinued early will be assigned the lowest available rank. All such subjects will be assigned the same value and thus the same rank will be assigned (i.e., treating each subject as a tie). The ranked ANCOVA will then be performed on this dataset. An estimate of the placebo-corrected median difference will not be provided for this analysis.

An additional sensitivity analysis will be conducted by repeating the primary analysis on the PPS population.

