### 3.2 Study Indication(s)

Treatment with gemcabene is indicated as an adjunct to diet to reduce serum triglyceride (TG) levels in adult patients with severe hypertriglyceridemia ( $\geq 500$  mg/dL); where lowering TG levels below 500 mg/dL may decrease a patient's risk for developing pancreatitis.

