## 6.2 Endpoints

### 6.2.1 Primary Endpoint

The primary efficacy endpoint is the percent change in fasting serum TG from baseline to end of study (EOS).

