Change from baseline (CFBL) for a given parameter (eg, y) for a given subject will be calculated as  $y_t - y_b$ , where  $y_t$  is a given subject's value  $t$  weeks post-baseline and  $y_b$  is a given subject's value at baseline. CFBL will be computed for subjects with a baseline value and a post-baseline value. In order to be included in a CFBL analysis for a given parameter, a subject must have a baseline value. If a subject does not have a baseline value, they will be excluded from the CFBL analysis. Percent CFBL for a given subject and parameter will be computed as  $\left(\frac{y_t - y_b}{y_b}\right) * 100$  (ie, CFBL divided by the baseline value and multiplied by 100). Percent CFBL will only be computed for subjects with a CFBL value. Additionally, subjects with a value of 0 at baseline will not have percent CFBL computed.

For efficacy parameters, end of treatment is defined as the last non-missing post-baseline value collected while on treatment or within 2 days of treatment (last dose) for a given subject. For safety parameters, end of treatment is defined as the last non-missing post-baseline value collected while on treatment or within 5 days of last dose.

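### SAP 11.2 gives early discontinuers the lowest rank of percent TG change, which is the best outcome, so the only dropout stress test rewards dropping out

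*SAP*

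**What the plan says.** The primary endpoint is percent change in fasting TG from baseline to EOS (SAP 6.2.1). SAP 9.2 fixes its sign: "Percent CFBL for a given subject and parameter will be computed as" (y_t − y_b)/y_b × 100, so a fall in TG is negative. The drug is intended as an "adjunct to diet to reduce serum triglyceride (TG) levels in adult patients" (Protocol 3.2), so lower is better.

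SAP 11.1 fits an ANCOVA "with percent change from baseline to EOS in TG (converted to ranks) as the dependent variable", with treatment, statin use and ranked baseline TG as predictors. The ranking rule is: "All values will be ranked by visit regardless of treatment group, with ties receiving the average of the ranks". It covers pooling and ties. It mentions neither a change of sign nor a descending order.

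SAP 11.2 then plans two sensitivity analyses:

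- The same ranked ANCOVA, in which "all subjects from the FAS who discontinued early will be assigned the lowest available rank". On ties it adds: "All such subjects will be assigned the same value and thus the same rank will be assigned". No placebo-corrected median difference is to be reported from this analysis.
- The primary analysis repeated on the Per-Protocol Set, which under SAP 8.2 requires completion of the 12 weeks.

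The primary analysis itself handles subjects with neither a Week 10 nor a Week 12 value by LOCF of the last on-treatment value (SAP 9.4).

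**The concern.** Giving all discontinuers one extreme tied rank only makes sense as a penalty: it asks whether the LOCF result survives if every dropout is counted as a failure. Ranked as SAP 11.1 describes, the low end of the scale is the good end, so the rule counts every dropout as a success.

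The protocol supplies a sharp example. Under Protocol 8.1.4.4, a subject whose TG remains at or above 2000 mg/dL stops study medication and completes the early termination visit. SAP 11.2 would then rank that subject as having the largest TG reduction in the study.

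If an active arm loses more subjects, for instance to adverse events, the analysis creates apparent benefit for that arm. If placebo loses more, it hides benefit. In neither case can it show that the primary result is robust to dropout. The Per-Protocol rerun does not fill the gap because it leaves the discontinuers out. With no effect estimate reported, a reader of the output would also have little to reveal that the direction was wrong.

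**Working it through.** **Inputs from the SAP.** 30 randomized per arm, 1:1:1; SD 43; difference of 35 points; two-sided α = 0.05; 80% power; 15% dropout (SAP 7.1 and 9.1).

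**The plan's own figure.** A two-sample t-test with a difference of 35 and SD 43 needs 25 evaluable per arm (power 80.5%; 24 gives 78.8%). Then 25/(1 − 0.15) = 29.4, rounded up to 30. The stated sample size is reproduced.

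**Direction.** Percent changes of −60, −40, −20, 0 and +20 receive ascending ranks 1, 2, 3, 4 and 5. The lowest rank belongs to the largest reduction.

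**Shift under no drug effect, by hand.** Take 13 discontinuers among 90 (14.4%, close to the planned 15%), split 2 on placebo, 7 on 300 mg and 4 on 600 mg.

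- *Lowest rank.* The 13 tied subjects share rank (1 + 13)/2 = 7. The other 77 average (14 + 90)/2 = 52. Mean rank on 300 mg is (7×7 + 23×52)/30 = 41.5; on placebo it is (2×7 + 28×52)/30 = 49.0. Difference: −7.5, in favour of drug.
- *Highest rank.* The tied rank is (78 + 90)/2 = 84 and the others average 39. Mean rank on 300 mg is (7×84 + 23×39)/30 = 49.5; on placebo it is (2×84 + 28×39)/30 = 42.0. Difference: +7.5, against drug.

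The gap between tied and untied mean ranks is 45 in both cases, so each excess discontinuer moves the comparison by 45/30 = 1.5 ranks.

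**Simulation of the SAP model.** Rank of percent change was regressed on treatment, statin and ranked baseline. There were 3,000 trials per row, with ascending ranks and ties averaged. Discontinuers were set to one value below the observed minimum (lowest rank) or above the observed maximum (highest rank). Entries are the probability of a significant result favouring 300 mg over placebo; the nominal value under no effect is 2.5%.

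| True effect (points) | Discontinuers placebo/300/600 | No dropout | Lowest rank | Highest rank |
|---|---|---|---|---|
| 0 | 4/4/4 | 3.0% | 1.0% | 1.2% |
| 0 | 2/7/4 | 2.5% | 14.7% | 0.0% |
| 0 | 1/8/4 | 2.7% | 29.1% | 0.0% |
| 0 | 7/2/4 | 2.8% | 0.0% | 14.9% |
| 20 | 2/7/4 | 40.6% | 69.6% | 0.6% |
| 35 | 4/4/4 | 84.8% | 62.8% | 63.2% |
| 35 | 2/7/4 | 85.2% | 96.5% | 10.4% |
| 35 | 7/2/4 | 85.3% | 5.6% | 95.1% |

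The Monte Carlo standard error is at most about 0.9 points. The simulated mean rank differences for 2/7/4 under no effect were −7.6 and +7.4, matching the hand calculation.

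**How the error grows with imbalance.** These runs used no effect, the lowest rank, 4 discontinuers on 600 mg and 4,000 trials each. False significant benefit for 300 mg, by discontinuers on 300 mg vs placebo:

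| 4 vs 4 | 5 vs 4 | 6 vs 4 | 6 vs 3 | 7 vs 2 | 8 vs 1 |
|---|---|---|---|---|---|
| 0.9% | 1.4% | 2.6% | 4.8% | 13.7% | 29.4% |

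Repeat runs gave 3.1% for 6 vs 4 and 6.2% for 6 vs 3.

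**The case against.** **The order of ranking is not stated.** The SAP says neither ascending nor descending, the ranking step is not in the printed code, and the authors may have used lowest to mean worst. This is fair as to intent. But that reading needs descending ranks, which appear nowhere, and ascending order is the natural meaning of converting values to ranks. Even on the charitable reading, two programmers could deliver opposite results from the same sentence, so it needs correcting either way.

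**The large figures need lopsided dropout.** This stands. The documents give one pooled rate of 15% and no rate by arm. At 6 vs 4 the false-benefit rate is about nominal, and 29% is the top of the range shown.

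**Worst-rank scoring is itself extreme.** Also true. Under no effect with 7 vs 2, the highest rank gives a significant result favouring placebo in 13.9% of trials, and with the imbalance reversed it favours drug. It is a deliberate penalty on the arm that loses more subjects, not an unbiased estimate. That penalty is what a stress test of LOCF is for, and the sentence as written supplies the opposite.

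**The reach is limited.** The primary analysis, the Hodges-Lehmann estimates and the secondary analyses are untouched. No decision rule is attached to this analysis, and subjects with no post-baseline efficacy value are outside the FAS. All of that is correct. It limits the consequence without making the analysis usable.

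**Conclusion.** The concern holds. Read with ordinary ascending ranks, SAP 11.2 scores every early discontinuer in the FAS at the best end of the scale, and no other planned analysis tests dropout adversely.

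Each excess discontinuer on an active arm shifts the mean rank comparison by 1.5 ranks towards drug, where a penalty would shift it 1.5 ranks the other way. At 7 vs 2 discontinuers this is the difference between 14.7% and 0.0% false benefit under no effect, and between 96.5% and 10.4% significance under a true 35-point effect. With balanced dropout the choice makes almost no difference.

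The simulated figures assume the splits of dropout by arm shown above, normal percent changes with SD 43, and dropout, baseline and statin use unrelated to outcome. The direction of the error depends on none of these, only on ascending ranks. It must be corrected, because as written the analysis can make a fragile result look robust.

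**What to change.** Replace the rule in SAP 11.2 with wording to this effect: *ranks are assigned in ascending order, so that a low rank means a greater TG reduction; all FAS subjects who discontinued early receive one common value larger than the largest observed percent change from baseline in TG, and so share the highest (worst) rank.* State the ascending order in SAP 11.1 as well, so that both analyses use the same convention.

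The cost is one sentence and one line of code. The sensitivity result may look less favourable if dropout is higher on drug. The change should be made before the treatment codes are requested after the last Week 12 visit (SAP 4.1), because a direction settled after that could be seen as chosen from the data.
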